8.4 Assessment of Safety Events

AE information collected will include event description, date of onset, assessment of severity and relationship to study product and alternate etiology (if not related to study product), date of resolution of the event, seriousness and outcome. The assessment of severity and relationship to

the study product will be done only by those with the training and authority to make a diagnosis and listed on the Form FDA 1572 as the site principal investigator or sub-investigator. AEs occurring during the collection and reporting period will be documented appropriately regardless of relationship. AEs will be followed through resolution.

SAEs will be:

- Assessed for severity and relationship to study product and alternate etiology (if not related to study product) by a licensed study physician listed on the Form FDA 1572 as the site principal investigator or sub-investigator.
- Recorded on the appropriate SAE report form, the medical record and captured in the clinical database.
- Followed through resolution by a licensed study physician listed on the Form FDA 1572 as the site principal investigator or sub-investigator.

An abnormal laboratory value which cannot be attributed to chemotherapy for malignancy will be recorded in the database as an AE **only** if the laboratory abnormality is characterized by any of the following:

- Results in discontinuation from the study
- Is associated with clinical signs or symptoms
- Requires treatment or any other therapeutic intervention
- Is associated with death or another serious adverse event, including hospitalization.
- Is judged by the Investigator to be of significant clinical impact
- If any abnormal laboratory result is considered clinically significant, the investigator will provide details about the action taken with respect to the study intervention and about the participant's outcome.

8.5 Reporting of Serious Adverse Events

Any AE that meets protocol-defined serious criteria or meets the definition of Adverse Event of Special Interest that require expedited reporting must be submitted immediately (within 24 hours of awareness) to OSRO Safety using the CCR SAE report form.

All SAE reporting must include the elements described in section [8.4](#)

SAE reports will be submitted to the Center for Cancer Research (CCR) at: [contact] and to the CCR PI and study coordinator. CCR SAE report form and instructions can be found at: <https://ccrod.cancer.gov/confluence/pages/viewpage.action?pageId=157942842>

Following the assessment of the SAE by OSRO, other supporting documentation of the event may be requested by the OSRO Safety and should be provided as soon as possible.

8.6 Safety Reporting Criteria to the Pharmaceutical Collaborators

Reporting will be per the collaborative agreement.

8.7 Reporting Pregnancy

8.7.1 Maternal exposure

Pregnant women are excluded from enrolling due to the possible deleterious effects of the investigational vaccine on the fetus.

If a participant becomes pregnant during the course of the study, the pregnancy will be reported to the Sponsor no later than 24 hours of when the Investigator becomes aware of it. If a pregnancy occurs while on study, to minimize the risks the subject will be withdrawn from the study and follow up care continued by their home obstetrics/gynecological (OB/GYN) doctor.

No inducements, monetary or otherwise, will be offered to terminate a pregnancy. No individuals engaged in the research will have any part in the decisions as to the timing, method, or procedures used to terminate a pregnancy and individuals engaged in the research will have no part in determining the viability of a neonate.

Pregnancy itself is not regarded as an SAE.

The outcome of all pregnancies should be followed up and documented per stand of care. The investigator should notify the Sponsor no later than 24 hours of when the outcome of the pregnancy becomes known.

8.7.2 Paternal exposure

Male participants should refrain from fathering a child or donating sperm during the study and use effective contraception from first vaccination until 30 days after the last vaccination.

Pregnancy of the participant's partner is not considered to be an AE. However, the outcome of all pregnancies occurring from the date of the first vaccine dose until 1 month after the last dose should, if possible, be followed up and documented. Pregnant partners may be offered the opportunity to participate in an institutional pregnancy registry protocol (e.g., the NIH IRP pregnancy registry study) to provide data about the outcome of the pregnancy for safety reporting purposes.

8.8 Regulatory Reporting for Studies Conducted Under CCR-Sponsored IND

Following notification from the investigator, CCR, the IND sponsor, will report any suspected adverse reaction that is both serious and unexpected. CCR will report an AE as a suspected adverse reaction only if there is evidence to suggest a causal relationship between the study product and the adverse event. CCR will notify FDA and all participating investigators (i.e., all investigators to whom the sponsor is providing drug under its INDs or under any investigator's IND) in an IND safety report of potential serious risks from clinical trials or any other source, as soon as possible, in accordance to 21 CFR Part 312.32.

All serious events will be reported to the FDA at least annually in a summary format.

8.9 Halting Rules

8.9.1 Study Halting Criteria

If any of the below occurs, the Protocol Chair will halt accrual to the trial to conduct a detailed safety review. Prior to resumption of the study, an expedited safety report will be sent to and reviewed by FDA if requested. All events also must be evaluated by the SMC.

- Any participant experiences laryngospasm, bronchospasm or anaphylaxis within 24 hours after administration of vaccine that is considered related to vaccine.
- Two (2) or more participants experience an allergic reaction such as generalized urticaria defined as occurring at three or more body parts within 72 hours after administration of vaccine that is considered related to vaccine.
- Any participant experiences suspected or confirmed myocarditis and/or pericarditis related to the study vaccine within 6 weeks of administration.
- Any serious adverse event deemed related to the vaccine will result in a halt to study accrual and an ad hoc meeting of the Safety Monitoring Committee (SMC). After a discussion of the event, the decision will be made as to whether to halt further accrual or lift the hold on accrual, based on the facts of the case and emerging evidence. Participants already on trial who successfully completed the first dose without incident will be allowed to receive the second dose of the vaccine, as per the mRNA-1273 vaccine's Emergency Use Authorization (EUA) granted in December 2020.

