| SOP | Standard Operating Procedure |
| SUSAR | Suspected Unexpected Serious Adverse Reaction |
| US | United States |
| WHO | World Health Organization |

PROTOCOL SUMMARY

Title: A Trial of the Safety and Immunogenicity of the COVID-19 Vaccine (mRNA-1273) in Participants with Hematologic Malignancies and Various Regimens of Immunosuppression, and in Participants with Solid Tumors on PD1/PDL1 Inhibitor Therapy, Including Booster Doses of Vaccine

Design of the Study: This is an open-label, multicenter clinical trial designed to evaluate the safety, reactogenicity and primary immunogenicity of the mRNA-1273 vaccine administered in 2 doses, 28 days apart, in participants who have hematological malignancy and are immunosuppressed due to their disease and/or treatment or receiving a PD-1/PDL-1 inhibitor for treatment of a solid tumor can be associated with appropriately high rates of development of neutralizing antibodies of mRNA-1273. The trial will also evaluate the safety, reactogenicity and immunogenicity after administration of additional “booster” doses of the vaccine.

Study Phase: 2

Study Population: For the vaccine-naïve cohorts, up to 80 participants will be enrolled.

- 20 participants with solid tumor malignancies who have initiated PD1/PDL1 inhibitor therapy as part of standard of care and are deemed to have a stable regimen without the need for any immunosuppressive therapy or corticosteroids.
- 60 participants with leukemia, lymphoma, multiple myeloma and participants post-allogeneic stem cell transplant will be enrolled based on their perceived risk of immunosuppression.

For the previously-vaccinated (also known as “booster”) cohorts, up to 140 participants will be enrolled for booster injections. All participants on the vaccine-naïve cohorts will have the option of receiving boosters; however, they will not count towards the maximum accrual goal for each of the booster groups. Note: All participants will be eligible to receive up to three (3) booster doses of vaccine on study.

- 20 participants with solid tumor malignancies who have initiated PD1/PDL1 inhibitor therapy as part of standard of care and are deemed to have a stable regimen without the need for any immunosuppressive therapy or corticosteroids.
- 20 participants with chronic lymphocytic leukemia who are not currently on any therapies
- 20 participants with chronic lymphocytic leukemia who are on BTK inhibitor therapy alone

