6.1.3 Vaccine Administration and Follow-Up for Booster Vaccine Cohorts

Participants from the Vaccine-Naïve Cohorts who receive the additional booster will follow-up per the Booster Vaccine Cohort and will follow the below timeline. They will not be required to complete any Vaccine-Naïve Assessments after receiving the booster vaccine. They will become eligible for their respective booster per the Booster Vaccine Cohort 4 weeks after their second vaccination. A physical examination may be performed, as indicated, based on participant's recent clinical history, but for participants transitioning from the Vaccine-Naïve Cohorts, this will not be required. Similarly, baseline labs will not be required for Vaccine-Naïve participants who transition into the Booster Vaccine Cohorts.

Participants who enroll on trial after a previous booster vaccination off-trial will follow the same study calendar, as below, provided at least four weeks have passed from the last booster vaccination.

Similarly, participants who receive an initial booster vaccination from this protocol will be eligible for a second and a third booster vaccination and follow the study the same study calendar as below, provided at least four weeks have passed from the last booster vaccination. The date of

their second booster dose will be considered Day 1. If they receive a third booster dose on protocol, the calendar will be reset, and the date of their third booster will be considered Day 1.

6.1.3.1 Day 1, Visit 1, Booster Vaccine Dose 1

- Unless otherwise indicated, the following baseline evaluations can be performed within 28 days prior to vaccine administration. The screening evaluations and baseline evaluations may be performed on the same day. Any evaluations required at both timepoints will not need to be duplicated if this occurs. As noted above, participants who are transitioning from the Vaccine-Naïve cohorts will not need any baseline labs, as they are already enrolled on the protocol.
- Participants in the BTK inhibitor interruption arm must stop their BTK inhibitor therapy no later than Day -7 and may resume no sooner than Day 15.
- Eligibility baseline criteria for study entry and receipt of Dose 1 will be reviewed with the participant.
- Vital signs will be obtained, including weight, temperature, pulse, and blood pressure.
- Medical history will be reviewed to assure continued eligibility.

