6.1.3.6 Day 360, Visit 6 (+/- 28 days)

- In-person visit
- Follow-up interim medical history and vital signs will be completed.
- Unsolicited AEs, and SAEs, that have occurred since the last contact will be collected.
- Samples will be collected for immunology/correlative studies (see section [7.3](#)).
- Standard antibody testing to assess immune response
- Participants will be thanked for participating in the study
- If a participant elects to have a second or third booster vaccination on protocol, the date of administration of this dose will be considered Day 1. The minimum timeframe between booster vaccination doses will be 28 days. Day 360 timepoint, if not yet reached on the original booster vaccination on protocol will be timed according to the participant's last vaccination dose.

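### The halting rules in 8.9.1 automatically stop only accrual; no protocol text expressly holds optional boosters to enrolled participants until the SMC has reviewed the event.

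*Combined protocol and SAP*

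**What the plan says.** Section 8.9.1 lists four criteria: related anaphylaxis, laryngospasm or bronchospasm; two or more related allergic reactions; related myocarditis or pericarditis; and any related serious adverse event (SAE). If any occurs, "the Protocol Chair will halt accrual to the trial to conduct a detailed safety review". The section adds "All events also must be evaluated by the SMC" and "Prior to resumption of the study, an expedited safety report will be sent to and reviewed by FDA if requested". For a related SAE, the decision after discussion is put only as keeping or lifting the hold on accrual.

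One sentence in 8.9.1 deals with dosing of people already enrolled. It sits in the related-SAE criterion and rests on the December 2020 Emergency Use Authorization: "Participants already on trial who successfully completed the first dose without incident will be allowed to receive the second dose of the vaccine". Boosters are not mentioned.

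The Protocol Summary says "All participants will be eligible to receive up to three (3) booster doses of vaccine on study". Of vaccine-naïve participants who take a booster it says "however, they will not count towards the maximum accrual goal for each of the booster groups", and 6.1.3.1 says that they "will not need any baseline labs, as they are already enrolled on the protocol". The Day 360 visit (6.1.3.6) still provides for what happens "If a participant elects to have a second or third booster vaccination on protocol". Section 8.10.1 gives the SMC 1-2 weeks from reporting to meet about myocarditis or pericarditis. It states no deadline for the other criteria.

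**The concern.** An accrual halt acts on people entering the trial. A large share of the possible injections goes to people already in it, as optional repeat doses. Read literally, a new enrollee's first booster stops when a criterion is met, while an enrolled participant's elective booster may go ahead during the same unreviewed signal. Section 2.5.1 says that myocarditis and pericarditis have been reported most in younger men after a second dose, but also after other doses, so boosters carry the same type of risk. At stake is whether elective doses continue between a related event and the SMC's review of it. The question becomes sharper once accrual has closed, because the one automatic dosing-related action then has nothing to act on.

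**Working it through.** The plan gives no figure for this point, so there is none to reproduce. The check is of the text first, and then of the size.

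**Does any text hold optional boosters to other enrolled participants before SMC review?**

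| Place | What it does | Mandatory hold before review? |
|---|---|---|
| 8.9.1, opening | Halts accrual; requires safety review and SMC evaluation | No; acts on accrual only |
| 8.9.1, dose 2 sentence | Permits dose 2 after a related SAE | No; silent on boosters |
| 4.2.2 with 5.1 | Sends eligibility for later doses to the inclusion criteria | No; 5.1 has no safety-hold condition |
| 4.5 | Mentions a safety pause, about a missed dose 2 | No; undefined, not applied to boosters |
| 6.1.3.4 to 6.1.3.6 | Require 28 days between boosters | No; timing only |
| 6.3.1 and Appendix E | Remove a participant who had an event; allow investigator decision | No; individual or discretionary |
| 6.3.5 | Allows the study to be suspended | No; discretionary |
| 8.10.1 | SMC advises on continued product administration | No; follows the review |

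**How many optional doses could there be?**

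Inputs: 80 vaccine-naïve participants with up to 3 boosters each; 140 booster-cohort participants (Protocol Summary, Table 2) or 120 (section 3.1), each with up to 2 boosters beyond the first.

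- With 140: 80 × 3 + 140 × 2 = 240 + 280 = 520.
- With 120: 80 × 3 + 120 × 2 = 240 + 240 = 480.
- Participants boosted before entry receive a single dose (5.2.3). If a share f of the 140 were, the total is 240 + 280 × (1 − f): 380 at f = 0.5 and 240 at f = 1.
- Section 11.3.3 describes one optional booster in Arm 1 and only the Day 1 dose in Arm 2. Taken alone it gives 80 × 1 = 80, but the Summary and 3.1 both allow three.

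**How many would fall in one review?**

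Uptake u is not given. Assume that boosters are spread evenly over S days. The expected number in a review of d days is N × u × d / S. With d = 14 and S = 365:

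| N | u = 100% | 50% | 25% | 10% |
|---|---|---|---|---|
| 520 | 19.9 | 10.0 | 5.0 | 2.0 |
| 480 | 18.4 | 9.2 | 4.6 | 1.8 |
| 380 | 14.6 | 7.3 | 3.6 | 1.5 |
| 80 (11.3.3 alone) | 3.1 | 1.5 | 0.8 | 0.3 |

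A 7-day review halves each entry. For N = 520 and d = 14, S = 183 gives 39.8 at full uptake and 9.9 at 25%; S = 487 (16 months) gives 14.9 and 3.7.

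**Would a pause put any booster out of window?** No. The protocol sets a 28-day minimum between doses and states no maximum.

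**The case against.** The best contrary argument is the dose 2 sentence. If the halt touched only enrollment, permission to give dose 2 to people already on trial would be unnecessary. One can therefore read the halt as reaching all dosing, with dose 2 exempted and boosters not. The heading of 8.9.1, the reference to resuming the study, and the safety pause in 4.5 point the same way. This stands as evidence of possible intent, and a reader should not infer that the authors meant boosters to continue. It does not supply a rule: the permission appears under one criterion of four, the operative verb applies to accrual, and two sites could read the section differently.

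There are also real controls. Myocarditis, pericarditis, hypersensitivity and related SAEs are events of special interest (8.1.5), reportable within 24 hours (8.5). The team meets weekly while participants are being treated (16.6.1), and the booster visit reviews eligibility and history (6.1.3.1). Staff who know of an event can withhold a dose. So the 1-2 weeks is not a period without oversight, and it would be wrong to infer that it is. These controls nevertheless depend on someone choosing to act.

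The SMC charter was not available and may contain a hold. That limits the point to the protocol text.

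**Conclusion.** The point holds as a gap in the mandatory text. Section 8.9.1 automatically halts accrual and nothing else that bears on dosing, and no protocol text expressly holds optional boosters to other enrolled participants until the SMC has reviewed the event. After accrual closes, the safety review and SMC evaluation remain mandatory, but the accrual halt stops no injections.

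The size is modest. The 480-520 figure is a ceiling for the whole study, not a forecast; it assumes that everyone takes every optional dose and that nobody was boosted before entry. Plausibly only a few doses would fall in any one review. The window counts rest on assumed uptake and even spread, and the harm avoided is not quantified, because the documents give no per-dose risk.

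A reader might also infer that pausing boosters would break the limit on BTK inhibitor interruption in cohort 6. The documents do not support this. Section 2.4.5 sets the 3-week limit for each hold, and 4.6 ties the hold to a vaccination. A pre-dose hold cut short after 1 to 7 days, a restart, and a later 7 + 14 = 21-day hold are separate interruptions, none longer than 3 weeks.

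This is a cheap improvement to a safety rule. It does not challenge the trial's design or its analysis.

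**What to change.** Amend the opening sentence of 8.9.1 so that, when any criterion is met, the Protocol Chair both halts accrual and pauses optional booster injections to enrolled participants in both arms, until the SMC has reviewed the event and recommended that dosing proceed. Leave the dose 2 sentence unchanged. If the SMC charter already contains such a hold, a cross-reference in 8.9.1 is enough.

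The cost is one sentence of amendment text, with no change to sample size, visits or dose 2. Optional boosters would wait about 1-2 weeks after a myocarditis or pericarditis event. The wait could be longer under the other criteria, which have no stated SMC deadline. Some high-risk participants would be boosted later, and some might seek a booster off trial, without the protocol's ECG and troponin checks.

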8.10 Safety Oversight

8.10.1 Safety Monitoring Committee (SMC)

The SMC is an independent group of at least 3 experts that monitors participant safety and advises The Sponsor. SMC members will be separate and independent of study staff participating in this trial and should not have scientific, financial, or other conflicts of interest related to this trial. The SMC will consist of members with appropriate expertise to contribute to the interpretation of data from this trial. A quorum will consist of a simple majority.

Given the frequency and urgency to review data, the SMC will not need to meet unless halting rules are met.

SMC will meet to evaluate any adverse events associated with myocarditis or pericarditis within 1-2 weeks of reporting of the event.

Cumulative AE data will be provided to the SMC after all participants have completed Day 36.

The SMC will meet when trial halting criteria are met, or as requested by the sponsor or PI.

The SMC will have a final review meeting at the end of the study.

Procedures for SMC reviews/meetings will be defined in the SMC charter. The SMC will review applicable data, including, but not limited to, enrollment, demographics, dosing data, clinical laboratory data, and safety data, at scheduled timepoints during this trial as defined in the SMC charter. The SMC will review blinded aggregate data in the open session of the SMC meetings.

Additional data may be requested by the SMC, and interim statistical reports may be generated as deemed necessary and appropriate by the Sponsor. As an outcome of each review/meeting, the SMC will make a recommendation as to the advisability of proceeding with study product administration, and to continue, modify, or terminate this trial.

8.11 Sponsor Protocol Deviation Reporting

A Protocol Deviation is defined as any non-compliance with the clinical trial Protocol, Manual of Operational Procedures (MOP) and other Sponsor approved study related documents, GCP, or protocol-specific procedural requirements on the part of the participant, the Investigator, or the study site staff inclusive of site personnel performing procedures or providing services in support of the clinical trial.

Non-NIH participating sites not using the CCR Protocol Deviation Tracking System (PDTs) will report any protocol deviation on the OSRO Site Protocol Non-Adherence/Deviation Log, or a site-generated protocol deviation report approved by OSRO. The Non-Adherence/Deviation Log should be maintained in the site essential documents file and submitted to OSRO via [contact] on the first business day of each month throughout the study.

It is the responsibility of the study Staff to document any protocol deviation identified by the Staff or the site Monitor in the CCR Protocol Deviation Tracking System (PDTs) online application. The entries into the PDTs online application should be timely, complete, and maintained per CCR PDTs user requirements. In addition, any deviation to the protocol should be documented in the participant's source records and reported to the reviewing IRB per their guidelines. OSRO required protocol deviation reporting is consistent with E6(R2) GCP: Integrated Addendum to ICH E6(R1): 4.5 Compliance with Protocol; 5.18.3 (a), and 5.20 Noncompliance; and ICH E3 16.2.2 Protocol deviations.

